### Theme 1: Applying rTMS treatment and its evaluation by neuropsychological and clinical assessments

1. Recruit people (from Riverview Health Center and also from [name] referrals), who have had a head injury within the past two to 12 months, have a clear diagnosis of TBI, and have persistent post-TBI symptoms. Collect standard neuropsychological assessment data at baseline.

2. Enroll the study participants into a “Sham Group” and a “Treatment Group” with a three-week protocol, and apply the treatment.
3. Record spatio-temporal assessments before and after treatment sessions, and examine the efficacy of rTMS treatment on the post-TBI symptoms by standard clinical and neuropsychological assessments by statistical analysis.

Theme 2: Monitoring treatment efficacy by objective measures, EVestG and spatio-temporal assessments

4. Record EVestG data with all its seven current stimuli at baseline (before the treatment) and immediately after treatment and also four and eight weeks after the last treatment.
5. Analyze EVestG data for extracting the optimum measures (biofeatures) showing the changes due to rTMS treatment.
6. Optimize (reduce the number of stimuli if possible) the EVestG recording protocol upon the results of Objective 5.
7. Examine the statistical correlation of the EVestG biofeatures representing the TBI recovery with data from the clinical and neuropsychological assessments as well as spatio-temporal assessments (derived in Objective 3).

Theme 3: Evaluating the objective measures of EVestG and spatio-temporal assessments in Control group

8. Recruit 20 age-and-gender-matched individuals with no history of head injury and record their EVestG data four times with a similar schedule to that of TBI patients, and investigate the consistency of the EVestG data between the sessions and compare with those of people with TBI during treatment.
9. Run the spatio-temporal assessments at the same sessions of EVestG recording in the Control Group and examine the effect of learning on the performance in these assessments.

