### **Exclusion Criteria for all Participants**

- 1) Use of neuro- or psycho-active medications as published in recommendations [26]
- 2) Active use of illicit drugs
- 3) History of epilepsy
- 4) History of any other brain lesions including tumors, infectious, vascular, or metabolic lesions
- 5) Severe or recent heart diseases
- 6) Alcoholism
- 7) Pregnancy
- 8) The presence of metallic objects in the body; dental implants are fine but people with pacemakers are to be excluded; anything that is unsafe under MRI would be considered unsafe for TMS [26].
- 9) Lack of ability to adequately communicate (understand, read, speak) in English and understand the experimental protocol.
- 10) Pending litigation (i.e., patients with pending actions regarding disability reports, litigation, or other kinds of financial compensation).

Participants will receive the details of the study, and be asked to sign a written consent form prior to experiments. Upon meeting the eligibility criteria and providing informed consent, each patient participant will be randomly assigned to either treatment or sham groups; this assignment will not be revealed to the patients until the end of study. *The Sham Group's participants will be offered a course of treatment after the study is finished if the results show improvement beyond the placebo for the participants in Treatment Group.* Patients will be thoroughly assessed by the medical collaborators for their symptoms, and localization of the damage to the brain. The cognitively healthy Control Group will not receive any rTMS treatment. All participants will complete a series of cognitive and mental assessments, and EVestG assessments. The Control Group will go through a lesser number of questionnaires as there is no need for run concussion severity assessment on control group. The details of the study procedure are described below, and Table 1 summarizes the study protocol.

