### **EVestG Measurement**

All study participants (in all three groups) will go through four sessions of EVestG assessments: 1) before rTMS treatment, 2) after 12 sessions of rTMS treatment, 3) four weeks after the last rTMS treatment, and 4) eight weeks after the last rTMS treatment.

The subjects sit in a hydraulic chair with their eyes closed and head rested on the chair headrest; they receive a series of orthogonal passive whole body movement stimuli: up/down translation and a horizontal rotation to the right and return to center (RTC) in both sitting upright and supine positions, and side tilts to the right and left.

Each tilt and the rotation are about 40 degrees, while up/down movement are about eight inches; the movements are designed to be smooth with a constant acceleration/deceleration over 3s. The recordings are made in an acoustically attenuated (>30dB) and electromagnetically shielded chamber at the EVestG Lab, Riverview Health Center. The active gelled recording electrodes are TM-EcochGtrode (Bio-logic, France), and placed in both ears proximal to the eardrum. Reference electrodes (Biopac EL254S for earlobe and EL258S for forehead) are placed on the ipsilateral earlobes and a common ground electrode is placed on the forehead.

The left and right ears' signals are recorded using Spike2 software via a CED-1902 amplifier (60Hz notch filter, 10k gain, 1Hz high pass filter) and digitized using CED1401 ADC board at sampling rate of 41,666Hz. Each recording's duration was 60s for each stimulus: 20s stationary at the center position, 3s motion to a position (up or rotated), 17s stationary in that position, 3s return to the center, and another 17s of stationary recording in the center position.

The chair's position is also recorded simultaneously with the ear signals; it is used to extract the segments of interest for analysis. The particular segments of interest, shown in Figure 2, are: 1.5s immediately prior to the movement (BGi), 1.5s acceleration (onAA) and 1.5s deceleration (onBB) as well as the 1.5s segments from the return to the center: RTC BGi, RTC onAA and RTC

onBB. The acceleration/deceleration segments are selected as they give the largest differences compared to background. Each EVestG recording may take up to one hour.

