### **Custom Designed Visuo-Spatial and Spatio-Temporal Assessments**

Our custom designed visuo-spatial and spatiotemporal assessments include our virtual reality navigational orientation assessment [63].

[figure not shown]

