**Table 1: Treatment and Assessment Schedule**

Study Groups	Week	# of Treatments	Assessments
Treatment and Sham Groups	0 (Baseline)	None	EVestG, MoCA, MADRS, RPQ, Stroop, and spatiotemporal
	1	5 – Monday to Friday	None
	2	5 – Monday to Friday	None
	3	2 – Mon/Wed or Tue/Thu	None
	4		EVestG, MoCA, MADRS, RPQ, Stroop and spatiotemporal
	8		EVestG, MoCA, MADRS, RPQ, Stroop, and spatiotemporal
	12		EVestG, MoCA, MADRS, RPQ, Stroop, and spatiotemporal
Healthy Control Group	0		EVestG, MoCA, MADRS
	1		
	2		
	3		
	4		EVestG
	8		EVestG
	12		EVestG, MoCA, MADRS

**Figure 1.** Separation of mTBI and control subjects using two post potential features.

**Figure 2.** A) Sitting up/down movement, supine up/down movement, sitting horizontal rotation. B) Ear Electrode; C) Electrode placement; D) Subject connections.

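### Objective 9 needs the spatio-temporal test in healthy controls at every EVestG session, but Table 1 schedules it at none of their four visits

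*Combined protocol and SAP*

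**What the plan says.** Theme 3 of the Objectives is headed "Evaluating the objective measures of EVestG and spatio-temporal assessments in Control group". It holds two numbered objectives. Objective 8 recruits 20 matched controls and plans to "record their EVestG data four times with a similar schedule to that of TBI patients". Objective 9 adds the second measure: "Run the spatio-temporal assessments at the same sessions of EVestG recording in the Control Group and examine the effect of learning".

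The EVestG Measurement section confirms the number of sessions: "All study participants (in all three groups) will go through four sessions of EVestG assessments".

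Table 1 (Treatment and Assessment Schedule) differs. At weeks 0, 8 and 12 the Treatment and Sham rows read "EVestG, MoCA, MADRS, RPQ, Stroop, and spatiotemporal", and week 4 lists the same tests. The Healthy Control rows read "EVestG, MoCA, MADRS" at weeks 0 and 12, and list EVestG alone at weeks 4 and 8. The closing paragraph of the Exclusion Criteria section gives the table its standing: "Table 1 summarizes the study protocol".

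**The concern.** A learning effect can be measured only if the same people take the test more than once. Objective 9 provides for that; the visit schedule does not. Staff who book control visits from Table 1 would not run the test, and the omission could not be repaired later, because a first exposure to the test at baseline cannot be recreated.

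Two things would be lost. Objective 9, one of only two objectives under Theme 3, would have no data. The patients' results would also lack a healthy-control reference for practice. Patients take the test four times and Theme 2 uses it to monitor treatment efficacy, so some of any improvement may be familiarity with the task. The Sham Group does not isolate that part, because change under sham mixes practice with natural recovery and placebo response. The Introduction itself describes recovery continuing for up to two years after injury.

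The randomised comparison is not at stake: active and sham patients repeat the test equally often and at the same weeks.

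**Working it through.** The plan states no figure on this point, so the check is a comparison of sections and a count, followed by the precision that Objective 9 could achieve.

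**1. Schedule, section by section**

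| Place | Spatio-temporal test in controls |
|---|---|
| Objectives, Theme 3 heading | Named as part of the theme |
| Objective 9 | At every control EVestG session |
| Objective 8; EVestG Measurement | Four EVestG sessions for controls |
| Table 1, control rows, weeks 0 and 12 | Not listed (EVestG, MoCA, MADRS) |
| Table 1, control rows, weeks 4 and 8 | Not listed (EVestG alone) |
| Table 1, Treatment and Sham rows | Listed for patients at weeks 0, 4, 8 and 12 |
| Custom Designed Visuo-Spatial and Spatio-Temporal Assessments | Describes the test ("spatiotemporal assessments include our virtual reality navigational orientation assessment") but names no group or visit |

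**2. Is the table damaged?** It does not appear to be. The four control EVestG entries match the EVestG Measurement section. The MoCA and MADRS entries at the first and last visits match the section on Standard Neuropsychological and Screening Measures. Only the test named in Objective 9 is absent.

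**3. Count of assessments, before dropout**

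- Controls under Objective 9: 20 x 4 = 80, giving 3 session-to-session changes per control.
- Controls under Table 1: 20 x 0 = 0.
- Patients under Table 1: (10 + 10) x 4 = 80.

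**4. Precision if the data are collected.** For one within-person change between two sessions, the 95% confidence interval half-width in units of the SD of change is t(0.975, n-1)/sqrt(n).

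- n = 20: 2.093/4.472 = 0.468.
- n = 16: 2.131/4 = 0.533.

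The change detectable by a paired t-test (two-sided alpha 0.05, 80% power) is 0.66 SD at n = 20 and 0.75 SD at n = 16. The 16 completers reflect an assumed 20% dropout; the documents give no rate. If all three successive changes were tested with a Bonferroni split (alpha 0.05/3), the detectable change at n = 20 would be about 0.78 SD.

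These figures hold for any paired change at these sample sizes. They show that Objective 9 could be answered for moderate to large practice effects. The contradiction itself does not depend on them.

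**The case against.** The strongest reply is that this is a clerical omission from a summary table. Objective 9 and the Theme 3 heading are explicit, EVestG is recorded in a single laboratory, and the test is the team's own, so the investigators may well run it in controls whatever Table 1 says. The study is a pilot, this is the last of nine objectives, and it concerns a non-randomised group. This limits the consequence: loss of the data is conditional on Table 1 being followed, and the documents do not show how likely that is. It does not remove the contradiction.

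Other text bears on which version was intended. Study Population/Participants recruits the volunteers as controls for EVestG, which leans towards Table 1. The Standard Neuropsychological and Screening Measures section limits controls to MoCA and MADRS, which also fits Table 1, but that limit concerns standard measures and this test has its own section. The Exclusion Criteria section says that all participants complete cognitive assessments, which leans the other way. It also explains why controls answer fewer questionnaires: concussion severity need not be assessed in them. That reason does not explain leaving out a navigation task, but since the task is not a questionnaire, it is not evidence of intent either. None of these settles the question, so leaving the test out of the control group may have been deliberate.

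It is also fair to say that the SD-based figures are generic. The test's score and variability are not given, so they cannot be turned into points on the scale.

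**Conclusion.** The concern holds. Objective 9 and Table 1 cannot both be followed: the first calls for 80 control assessments and the second schedules none. If Table 1 governs, a numbered objective has no data and the patients' repeat results have no healthy-control reference for practice. The randomised active-versus-sham comparison is unaffected.

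The count rests only on the planned numbers of controls and sessions. The precision figures assume roughly normal changes, and the lower sample size assumes 20% dropout. The contradiction should be corrected before control visits begin, since the baseline test cannot be recovered afterwards.

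**What to change.** Reconcile Theme 3 of the Objectives with Table 1 in one of two ways.

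**(a) Keep the objective.** Add the spatio-temporal test to the Healthy Control rows of Table 1 at weeks 0, 4, 8 and 12. State the groups and visits in the section that describes the test. Summarise session-to-session change in controls as a mean with a 95% confidence interval. Treat it as a reference for practice and not as an exact correction, because patients may learn at a different rate.

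**(b) Give up the objective.** If controls are not meant to take the test, revise Objective 9 and the Theme 3 heading to say so.

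Option (a) costs some wording plus one test at four visits that controls already attend. The added time per visit cannot be judged, because the test's duration is not stated and EVestG alone may take up to one hour. Option (b) costs wording only, but the learning question goes unanswered. Option (a) is preferable because it keeps what the protocol sets out to do.

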### **Research Plan and Methods**

The study will be performed as a pilot prospective, randomized, controlled, double blind, two parallel groups clinical trial (examining sham versus active treatment). At the end of the study, the active treatment will be offered to the Sham Group if the treatment is shown to be effective.

### **Study Protocol**

#### **Study Population/Participants**

A total of 20 individuals with a clear diagnosis of TBI within the last 12 months (as confirmed by their treating Neurologist, Psychiatrist or Medical Rehab Physiatrist, who are the co-investigators in this study) prior to the commencement of this study will be recruited from Riverview Health Center patient and [name] clinic patient population. Ten patients will be randomly assigned to **Treatment Group** and 10 others to **Sham Group**. Neither the patients, nor the clinical assessors will know the sham versus real treatment group assignment. In addition, as one of the objectives of this study is to evaluate the EVestG assessment as a

diagnostic and monitoring tool, 20 age-and-gender-matched cognitively healthy volunteers will be recruited as controls for the EVestG assessment. The healthy **Control Group**'s participants must not have any history of TBI and also meet other exclusion criteria for patients group listed below.

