### **Inclusion Criteria for Patients**

Participants must be of age 18-70 years, and have had TBI in the last 12 months prior to inclusion and presence of persistent TBI symptoms at the time of inclusion as confirmed by the co-investigator physicians.

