### **Data analysis**

**EVestG Biofeature Extraction** – The NEER algorithm [52] will be used to locate and extract vestibular neural events. The interval histograms of the neural events are also used to extract the basic statistical properties of the neural firings such as probability density function (pdf), mean and variance, as well as fractal dimension, kurtosis and skewness of the signal. The features extracted from all tilts will be investigated to determine biofeatures specific to a concussion. The extracted biofeatures, e.g. fractal dimension, kurtosis and skewness of the potentials' distribution, from the recorded signal will be compared between Sham and Treatment Groups.

[figure not shown]
**Statistical Analysis, Clustering, Decision Making and Validation** – After data collection, the multivariate Analysis of Variance (MANOVA) statistical test will be run to determine the significant differences of any of the extracted biofeature measures between the sessions and the Control Group and the Treatment and Sham Groups. In all instances, a p-value less than 0.05 is considered significant. Cross correlation analysis will also be used to find the correlation between these measures and the neuropsychological assessments scores. Once the statistically significant features among the groups are found, the classic approach of discriminant analysis with leave-one-out routine (for robust results in small size data) will be run to investigate whether concussion cases can be identified. An important issue to address is the membership assignment of the subjects. Since there may not be confirmed and solid clinical and neuropsychological assessments for the recovery from the TBI post-symptoms, we will also run unsupervised (blind) clustering of the objective measures followed by our recently developed diagnostic decision making algorithm to identify TBI recovery. The diagnostic and monitoring algorithms will be checked with the updated diagnoses of the clinical symptoms (by the referring physician) and the neuropsychological evaluations.

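### Controls are matched to patients on age and gender, but the planned MANOVA carries neither factor; if either predicts an EVestG feature, the TBI v Control test gives up power that two covariates would recover

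*Combined protocol and SAP*

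**What the plan says.** The matching is stated twice. Under Study Population/Participants, "20 age-and-gender-matched cognitively healthy volunteers will be recruited as controls for the EVestG assessment". The Objectives repeat it in objective 8 (Theme 3): "Recruit 20 age-and-gender-matched individuals with no history of head injury and record their EVestG data four times". Neither place says whether matching is one to one or by frequency, or how close in age a control must be.

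On the patient side the plan has "A total of 20 individuals with a clear diagnosis of TBI within the last 12 months", split 10 and 10 between Treatment and Sham. The patient inclusion criteria add that "Participants must be of age 18-70 years", so the matching factor has a wide spread.

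The analysis is in the Data analysis section, under the paragraph on statistical analysis, clustering, decision making and validation. There, the "multivariate Analysis of Variance (MANOVA) statistical test will be run to determine the significant differences of any of the extracted biofeature measures" between sessions and among the Control, Treatment and Sham groups. The threshold is uniform: "In all instances, a p-value less than 0.05 is considered significant". Features found significant among the groups then go into a discriminant analysis with leave-one-out. Age and gender do not appear in any described analysis, and neither does a matched set or pair.

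**The concern.** A factor used to match should normally be carried into the analysis. Matching makes the two groups alike on age and gender, so the difference in group means varies less from sample to sample than it would between unmatched groups. A test with only group and session terms does not register this. It leaves the variation due to age and gender in the error term and computes the standard error as if the groups had been drawn independently. The estimated difference is not biased by these factors, but its standard error is too large, and the test rejects less often than its nominal level allows.

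The stake is the choice of features. Statistical significance decides which biofeatures enter the discriminant analysis, so a real feature missed at that step is not available to that classifier. With 20 participants a side and no power calculation in the documents, the precision bought by matching is worth using.

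**Working it through.** The plan states no sample-size calculation, effect size or SD, so it has no figure to reproduce. For orientation, 20 v 20 at two-sided 0.05 has 80% power for a difference of about 0.89 SD (normal approximation).

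**Inputs from the documents:** 20 patients and 20 controls; matching on age and gender; ages 18 to 70; significance at 0.05. Two-sided testing is assumed, because sidedness is not stated.

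**Assumptions:** R², the share of a feature's variance explained by age and gender, of 0, 10, 20 or 30%; a true difference of 0.8 SD; close matching (gender exact, age within 2 years); one feature at one session, with the 20 patients taken as one group.

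**Step 1, standard error.** In SD units with n = 20 per group:

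- Reported by the unadjusted test: sqrt(2/20) = 0.316.
- True value under close matching: sqrt(2(1-R²)/20) = 0.316, 0.300, 0.283, 0.265.
- Reported/true = 1/sqrt(1-R²) = 1.00, 1.05, 1.12, 1.20.

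**Step 2, size.** The unadjusted test rejects only when the estimate exceeds 1.96 × (reported/true) true standard errors. The normal approximation gives a size of 5.0, 3.9, 2.8 and 1.9%. Simulation of the t-test gives 4.8, 4.0, 2.9 and 2.1%. The 4.8% at R² = 0 is simulation error around 5%. The adjusted test stays near 5% throughout.

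**Step 3, power at 0.8 SD.** For the adjusted test, the noncentral t with 36 degrees of freedom and noncentrality 0.8/(true SE) gives 69.2, 73.7, 78.6 and 83.7%, in agreement with simulation.

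| Assumed R² | Reported/true SE | Size, unadjusted | Power, unadjusted | Power, adjusted |
|---|---|---|---|---|
| 0% | 1.00 | 4.8% | 70% | 70% |
| 10% | 1.05 | 4.0% | 71% | 74% |
| 20% | 1.12 | 2.9% | 71% | 78% |
| 30% | 1.20 | 2.1% | 73% | 84% |

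**Step 4, worth in participants.** Increasing the group size until the unadjusted matched test reaches the adjusted power takes about 22, 23 and 25 to 26 per group at R² of 10, 20 and 30%. Against 20 per group, that is roughly 10% (22/20), 15% (23/20) and 25 to 30% (25/20 to 26/20) more participants, and none at R² = 0.

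**Step 5, price of adjusting.** In this two-group model the residual degrees of freedom fall from 38 to 36. Comparing the critical t values, adjustment gives a narrower interval once R² exceeds about 0.4%. A pair term leaves 19 degrees of freedom and breaks even only at about 6.5%.

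**The case against.** **The association is unknown.** No section reports how age or gender relates to any EVestG feature. A reader might infer that the error bars are too wide as a matter of fact. The documents do not support that: it is true only if R² is above zero, and at zero nothing is lost or gained. This stands, and it is why the result is conditional and the range starts at zero.

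**The test computed is not the test planned.** The plan has a multivariate test over three groups of 20, 10 and 10 and four sessions; the working is a two-group test of one feature at one session. Pooling the 20 patients is natural only at baseline, since the arms may differ later. This also stands. The direction carries over to each TBI v Control contrast, but the exact percentages do not.

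**Overall conservatism.** A reader might infer that feature selection as a whole will be too cautious. The documents do not establish this. They do not say that session is a within-person factor. If the four sessions were analysed as independent rows, group standard errors would be too small (reported/true about 0.73, 0.63 and 0.57 at assumed within-person correlations of 0.3, 0.5 and 0.7, before allowing for matching). That could offset or reverse the effect described here. Many features are also tested at 0.05 with no stated multiplicity control, and features separating Treatment from Sham count as well.

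**The size of the gain.** A reader might take 1/(1-R²) - 1 = 11, 25 and 43% as the sample-size equivalent at R² of 10, 20 and 30%. Those figures compare reported variances. Matching has already reduced the true variance of the difference, so the equivalent in power is the smaller one in Step 4.

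**Closeness of matching.** It is not stated. Looser matching moves the unadjusted size back towards 5%. Covariate adjustment remains suitable, because it then also removes residual imbalance.

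**Conclusion.** The point holds as a conditional one. The plan matches on age and gender and then leaves both out of the only stated test of group differences. For a single feature at a single session, if age and gender explain 10 to 30% of its variance, the unadjusted TBI v Control test has a size of about 4.0 to 2.1% instead of 5%. It gives up about 3 to 11 percentage points of power at 0.8 SD (74 - 71 = 3; 84 - 73 = 11). R², the 0.8 SD difference and close matching are all assumptions; at R² = 0 there is no loss.

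This does not describe the net behaviour of the whole MANOVA. The comparison is not biased by the matching factors, and the randomised Treatment v Sham comparison is not affected by the matching. It is a desirable refinement for a pilot study, justified mainly because adjusting costs almost nothing even when the association is absent.

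**What to change.** In the Data analysis section, state that every TBI v Control comparison of EVestG biofeatures includes age (continuous) and gender as covariates, and state in the population section whether matching is individual or by frequency. Covariates work under either scheme, so they are the better default; a pair term applies only to one-to-one matching and uses many more degrees of freedom.

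The cost is a sentence of analysis text and two residual degrees of freedom (38 to 36 in the two-group case). Both variables have to be known in order to match, so no new data are needed. Adjusting features for age and gender within each leave-one-out training fold is optional: it is a choice about the classifier and takes more work than a change of wording.

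The same edit is a good place to declare session a within-person factor. That is a separate matter, but the sign of the net error depends on it.
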